#### 9.3.4 Visit 4: Fit and Dispense MyDay Energys

Visit 4 occurs after Baseline MyDay Sphere data have been collected. At this visit, MyDay Energys will be fit dispensed. The following procedures will be conducted:

- Changes to health or medication (not required if completed on same day already)

258	100
259	100
260	100
261	100
262	100
263	100
264	100
265	100
266	100
267	100
268	100
269	100
270	100
271	100
272	100
273	100
274	100
275	100
276	100
277	100
278	100
279	100
280	100
281	100
282	100
283	100
284	100
285	100
286	100
287	100
288	100
289	100
290	100
291	100
292	100
293	100
294	100
295	100
296	100
297	100
298	100
299	100
300	100
301	100
302	100
303	100
304	100
305	100
306	100
307	100
308	100
309	100
310	100
311	100
312	100
313	100
314	100
315	100
316	100
317	100
318	100
319	100
320	100
321	100
322	100
323	100
324	100
325	100
326	100
327	100
328	100
329	100
330	100
331	100
332	100
333	100
334	100
335	100
336	100
337	100
338	100
339	100
340	100
341	100
342	100
343	100
344	100
345	100
346	100
347	100
348	100
349	100
350	100
351	100
352	100
353	100
354	100
355	100
356	100
357	100
358	100
359	100
360	100
361	100
362	100
363	100
364	100
365	100
366	100
367	100
368	100
369	100
370	100
371	100
372	100
373	100
374	100
375	100
376	100
377	100
378	100
379	100
380	100
381	100
382	100
383	100
384	100
385	100
386	100
387	100
388	100
389	100
390	100
391	100
392	100
393	100
394	100
395	100
396	100
397	100
398	100
399	100
400	100
401	100
402	100
403	100
404	100
405	100
406	100
407	100
408	100
409	100
410	100
411	100
412	100
413	100
414	100
415	100
416	100
417	100
418	100
419	100
420	100
421	100
422	100
423	100
424	100
425	100
426	100
427	100
428	100
429	100
430	100
431	100
432	100
433	100
434	100
435	100
436	100
437	100
438	100
439	100
440	100
441	100
442	100
443	100
444	100
445	100
446	100
447	100
448	100
449	100
450	100
451	100
452	100
453	100
454	100
455	100
456	100
457	100
458	100
459	100
460	100
461	100
462	100
463	100
464	100
465	100
466	100
467	100
468	100
469	100
470	100
471	100
472	100
473	100
474	100
475	100
476	100
477	100
478	100
479	100
480	100
481	100
482	100
483	100
484	100
485	100
486	100
487	100
488	100
489	100
490	100
491	100
492	100
493	100
494	100
495	100
496	100
497	100
498	100
499	100
500	100
501	100
502	100
503	100
504	100
505	100
506	100
507	100
508	100
509	100
510	100
511	100
512	100
513	100
514	100
515	100
516	100
517	100
518	100
519	100
520	100
521	100
522	100
523	100
524	100
525	100
526	100
527	100
528	100
529	100
530	100
531	100
532	100
533	100
534	100
535	100
536	100
537	100
538	100
539	100
540	100
541	100
542	100
543	100
544	100
545	100
546	100
547	100
548	100
549	100
550	100
551	100
552	100
553	100
554	100
555	100
556	100
557	100
558	100
559	100
560	100
561	100
562	100
563	100
564	100
565	100
566	100
567	100
568	100
569	100

### 9.3.6 Visit 6: Study Exit

Visit 6 is completed when the participant exits the study. This may occur after study completion (i.e. after Visit 5), or if the participant discontinues from the study. The following procedures will be conducted at this visit:

- Remove study lenses (if applicable)
- 
- 
- Study completion or discontinuation form (as appropriate)
  - If there are records entered into the clinic's own patient chart system the exit date should also be recorded on these source documents.
  - If the subject is being exited due to discontinuation, further details need to be recorded on the Study Exit Form
- Post-study follow-up visits will be scheduled if the Investigator judges this is necessary.
  - Post-study follow-up requirement (Y/N). If yes, the reason and date of the follow-visit must also be recorded.
- Remuneration

## 10 Adverse Events and their Reporting

---

### 10.1 Adverse Response Definitions

**Adverse Event (AE):** An AE refers to any untoward medical occurrence (sign, symptom or disease) in a trial subject that does not necessarily have a causal relationship with the study device. AEs may be classified as 'unanticipated adverse device effects,' 'serious AEs,' 'significant AEs,' or 'non-significant AEs,' as defined below. Adverse events can be ocular or non-ocular.

Classification	Definition
Serious Adverse Event	Those events that are life-threatening, or result in permanent impairment of a body function, or permanent damage to a body structure or necessitate medical (therapeutic) or surgical intervention to preclude permanent impairment of a body function or permanent damage to a body structure.
Unanticipated Adverse Device Effect	Adverse events in a clinical trial that were not previously identified in the protocol in terms of nature, severity, or degree of incidence. An Unanticipated Serious Adverse Device Effect is an unanticipated adverse event that is serious in nature and caused by or associated with the device and is considered reportable.
Significant Adverse Event	Those non-serious adverse events that occur with contact lens usage that are not sight-threatening but are usually symptomatic and may warrant therapeutic management and /or temporary or permanent discontinuation of contact lens wear.
Non-Significant Adverse Events	Those less severe non-serious adverse events that occur with contact lens usage that are not sight-threatening, may or may not be symptomatic and may warrant palliative management, such as ocular lubricants or temporary interruption of contact lens wear.

AE classification, coding (for reporting to the sponsor) and examples are provided in the following table of Contact Lens Adverse Event Classification and Reporting:

Code	Condition	Potential AE Classification	Reporting
01	Presumed infectious corneal ulcer	SERIOUS	
02	Permanent loss of $\geq 2$ lines of best spectacle corrected visual acuity (BSCVA)	SERIOUS	Notify sponsor as soon as possible, within 24 hrs ; IRB reporting as per requirements
03	Corneal injury that results in permanent opacification within central cornea (6mm)	SERIOUS	
04	Neovascularization within the central 6mm of cornea	SERIOUS	

05	Uveitis or Iritis	SERIOUS	
06	Endophthalmitis	SERIOUS	
07	Hyphema	SERIOUS	
08	Hypopyon	SERIOUS	
09	Persistent epithelial defect	SERIOUS	
00	Other serious event	SERIOUS	
11	Peripheral non-infectious ulcer (outside central 6mm)	SIGNIFICANT	
12	Symptomatic corneal infiltrative events	SIGNIFICANT	
13	Superior epithelial arcuate lesions (SEALs) involving epithelial split	SIGNIFICANT	
14	Any temporary loss of $\geq 2$ lines BSCVA for $\geq 2$ wks	SIGNIFICANT	
15	Corneal staining $\geq$ dense coalescent staining up to 2mm in diameter (i.e. moderate staining)	SIGNIFICANT	
16	Corneal neovascularization $\geq$ 1.0mm to 1.5mm vessel penetration (if 2 Grade change from baseline)	SIGNIFICANT	
17	Any sign and/or symptom for which subject is administered therapeutic treatment or which necessitates discontinuation of lens wear for $\geq 2$ weeks	SIGNIFICANT	Notify sponsor as soon as possible, within 5 working days; IRB reporting as per requirements
10	Other significant event	SIGNIFICANT	
21	Conjunctivitis: bacterial, viral, allergic	NON-SIGNIFICANT	
22	Papillary conjunctivitis if $\geq$ mild scattered papillae/follicles approximately 1mm in diameter (if 2 Grade change from baseline)	NON-SIGNIFICANT	
25	Asymptomatic corneal infiltrative events	NON-SIGNIFICANT	
26	Localized allergic reaction	NON-SIGNIFICANT	
27	Contact dermatitis	NON-SIGNIFICANT	
28	Any sign and/or symptom for which temporary lens discontinuation for $> 1$ day is recommended	NON-SIGNIFICANT	
20	Other non-significant sign and/or symptom	NON-SIGNIFICANT	

#### Normal or adaptive symptoms

Transient symptoms such as end-of-day dryness, lens awareness, itching or burning or other discomfort may occur with contact lens wear and may occasionally reduce wearing time. **These are not reported as adverse events unless they are unexpected in nature, severity or rate of occurrence.**

## 10.2 Procedures for Adverse Events

---

Treatment of an adverse event will depend on its nature and severity. Based on the clinical judgment of the investigator the subject may be referred to an ophthalmologist for treatment. The investigator will attempt to determine whether the reaction is related to the study device/procedure or a result of other factors.

An Adverse Event Form will be completed for each adverse event. If both eyes are involved, a separate Adverse Event Form will be completed for each eye. Whenever possible, the adverse event will be photo-documented.

Expenses incurred for medical treatment as part of study participation will be paid by the sponsor (bills and prescription receipts kept). The subject must be followed until resolution and a written report completed indicating the subsequent treatment and resolution of the condition.

## 10.3 Reporting Adverse Events

---

All potential **Serious and Unanticipated Adverse Device Effects** that are related or possibly related to subject participation in the investigation will be reported to the Principal Investigator and to the designated medical monitor of the sponsor within 24 hours of the investigator becoming aware of the event. The Principal Investigator will report the event to the EC/IRB as soon as possible (by fax, mail/delivery, phone, or email), but within 10 business days of becoming aware of the problem. *All fatal or life threatening events will be reported immediately to the IRB.*

**Significant and Non-Significant Adverse Events** will be reported to the sponsor and the study coordinator as soon as possible, but no later than 5 working days after the occurrence.

Sponsor medical monitor contact details are:

Contact: [name], CooperVision  
Email: [[contact]](mailto:[contact])  
[contact] / [contact]  
Address: [name].  
[name]

## 10.4 Discontinuation from the Study

---

All discontinuations will be fully documented on the appropriate CRF Exit and Adverse Event forms as needed. Participants will be followed until resolution and they are free of the study-related complications or other ocular pathology, where possible. When possible, the study lenses involved in an Adverse Event will be returned to the sponsor in a new tightly sealed contact lens case, and labeled with the subject's study ID number and stored in multipurpose solution.

## **11 Statistical Analysis**

---

### **11.1 Statistical analysis**

---

Descriptive statistics will be provided on information regarding baseline variables (e.g., age, gender). Differences between lenses and over time will be compared using Paired t-tests. Paired t-tests /analysis of variance for normal (interval/continuous) data. The appropriate test will be selected based on tests of normality. Means and standard deviations will be provided for each variable.

All participants who were evaluated will be used in the analysis. In the event of missing data, individual data points will be excluded in the analysis and not extrapolated from the collected data.

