## 2 Study Objective

---

[figure not shown]
The aim of this study is to determine if habitual or adapted wearers of MyDay Sphere lenses can be confidently refit into MyDay Energys lenses and be successful after one week of daily wear.

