#### **Inclusion criteria**

A person is eligible for inclusion in the study if he/she:

- Is between 18 and 35 years of age (inclusive)
- Has read and signed the informed consent letter
- Is willing and anticipated to follow instructions and maintain the appointment schedule
- Habitually wears soft spherical contact lenses with a power between -1.00D to -6.00D (inclusive) for a minimum 5 days per week, 10 hours per day and anticipates no difficulty wearing contact lenses for 7 days per week, 10 hours per day.
- Habitually wears or is able to be adequately refit into MyDay Sphere lenses
- Demonstrates an acceptable fit with the study lenses
- Is correctable to a distance visual acuity of 0.20 logMAR (approximately 20/30) or better (in each eye) with the study contact lenses
- Uses digital devices, (e.g. computer, tablet, smart phone, iPad), for more than 4 hours a day, 5 days a week.
- Manifest cylindrical spectacle refraction does not exceed -0.75DC in either eye
- Has clear corneas and no active ocular disease
- Has a contact lens refraction that fits within the available parameters of the study lenses.

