### 9.2.1 Contact lenses

All subjects will be trial fitted and, if suitable, dispensed the MyDay Sphere and the MyDay Energys lens brand. The study lenses will be provided by the Sponsor. Details of the contact lenses are shown in Table 1.

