**Table 2: Summary of visits**

Visit code	Visit schedule	Visit Description	Duration (hrs)
1		Screening to determine eligibility and to establish optimum power of MyDay Sphere	1 (1.5 if fitting both lenses)
2*		Dispense MyDay Sphere**	0.5
3	≥7 days after V1	Review MyDay Sphere and baseline data collection	0.5
4		Fit and Dispense MyDay Energys***	0.5
5	7-10 days after V2	Review MyDay Energys	1
6		Study exit****	

\*Note: Visit 2 is only necessary if a change in MyDay Sphere lens power is required, or if a fit with MyDay Sphere is required for adaptation

\*\*Note: Visit 2 can be concurrent to Visit 1

\*\*\*Note: Visit 4 is concurrent to Visit 3

[figure not shown]
\*\*\*\*Note: Visit 6 can be concurrent to Visit 5

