### 9.3.3 Visit 3: Baseline MyDay Sphere review

Visit 3 occurs  $\geq$ 7 days after visit 2. The following procedures will be conducted during this visit to determine the baseline MyDay Sphere performance:

[figure not shown]
- Changes to health or medication

[figure not shown]
- Fit assessment of MyDay Sphere

[figure not shown]
- Centration: Optimum, decentration acceptable, decentration unacceptable

- Post-blink lens movement, 0-4, 1 step, 0 = Insufficient, unacceptable movement

[figure not shown]

- Overall fit acceptance 0-4, 0.5 step, 0 = Should not be worn

- If overall fit acceptance  $\leq 2$ , provide reason

- Remove contact lenses

- Participant continues right away with Visit 4

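### A participant who stops Energys for a fit-related reason before Visit 5 leaves the one-week paired test, and no visible analysis counts that person as a failed refit

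*Combined protocol and SAP*

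**What the plan says.** All references are to the combined protocol and SAP.

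- **Aim (section 2):** to find out whether Sphere wearers "can be confidently refit into MyDay Energys lenses and be successful after one week of daily wear".
- **Hypothesis (3.1):** a difference between the two lenses in overall fit acceptance grade.
- **Analysis (11.1):** paired t-tests or analysis of variance, with means and standard deviations. On the analysis set: "All participants who were evaluated will be used in the analysis". On gaps: "In the event of missing data, individual data points will be excluded in the analysis and not extrapolated from the collected data". No success proportion, count of failed refits or analysis of discontinuations is named.
- **Timing:** the baseline Sphere grade is taken at Visit 3 (9.3.3), after which "Participant continues right away with Visit 4". The Energys grade is taken at Visit 5, after 7 to 10 days of wear (9.3.5).
- **Early exit:** 9.3.6 provides for participants who discontinue. Their reasons and details go into the enrollment log (9.1) and the exit and adverse event forms (9.3.6, 10.4).
- **Cohort:** 5.1 sizes the study to allow for drop-outs and for deviations that affect who is analysed. Section 12.1 settles the cohort in a discussion before data export, with attention to deviations and adverse events. Neither participant nor investigator is masked (9.2.7).

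**The concern.** Someone who is dispensed Energys and gives it up within the week because of the fit is a negative answer to the question in section 2. Under 11.1 that answer appears as a missing value and is left out. The paired mean then describes completers only, and a reader cannot tell from it how many refits failed.

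The cohort wording adds a second, separate uncertainty. Section 11.1 reads as including everyone evaluated, while 5.1 and 12.1 leave room for exclusions. Nothing says on what grounds, and the people deciding may know both the lens and the result.

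**Working it through.** **1. The plan's own figure.** Section 5.1 gives a difference of 0.16, SD 0.4, alpha 0.05, n = 73 and power 92%. Reading 0.4 as the SD of the paired differences, with a two-sided test, the noncentrality is (0.16/0.4) × √73 = 3.42. The noncentral t distribution then gives 92.1%, so the figure reproduces. The allowance is 80 − 73 = 7 participants, or 7/80 = 8.75%. Losses of that size are already provided for, so the issue is who is lost and not power.

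**2. One participant followed through the visits.**

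| Step | Fit-related stop before Visit 5 |
|---|---|
| Visit 3, Sphere grade | present |
| Visit 4, Energys dispensed | yes |
| Visit 5, one-week Energys grade | absent |
| Paired difference | cannot be formed |
| Handling under 11.1 | excluded, not imputed |
| Reason for stopping | recorded on forms; no analysis named |

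**3. What a count would show.** The number of stops, k, is an assumption, because the documents give none. Assume also 80 dispensed (5.1) and every completer successful. The proportion is (80 − k)/80, with a Clopper-Pearson interval.

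| k | Successfully refit | Exact 95% CI | Completers only |
|---|---|---|---|
| 0 | 80/80 = 100% | 95.5 to 100 | 100% |
| 1 | 79/80 = 98.8% | 93.2 to 99.97 | 79/79 = 100% |
| 4 | 76/80 = 95.0% | 87.7 to 98.6 | 76/76 = 100% |
| 7 | 73/80 = 91.3% | 82.8 to 96.4 | 73/73 = 100% |

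The last row uses the whole loss allowance, which also covers deviations and unrelated drop-outs. Section 6.1 speaks of 80 completing. On that reading four stops would give 80/(80 + 4) = 95.2%, so the choice hardly matters.

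**4. Would the paired test show the stops if they were scored?** Assume completers have mean change 0 and SD 0.4, and each of k stops is scored d grades lower.

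- Mean: x = −k·d/80.
- Variance: [(79 − k) × 0.16 + (80 − k) × x² + k × (−d − x)²]/79.
- k = 4, d = 1: x = −0.05; variance (12 + 0.19 + 3.61)/79 = 0.200; SD 0.447; t = −1.00; p = 0.32.
- k = 4, d = 2: x = −0.10; variance (12 + 0.76 + 14.44)/79 = 0.344; SD 0.587; t = −1.52; p = 0.13.
- k = 4, d = 3 or 4: p = 0.083 or 0.066.
- k = 7, d = 2: p = 0.025.

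So with completers unchanged, a handful of stops would not make the test significant even if included, though seven could. The answer also depends on the assumed change in completers. If they improved by 0.16, four stops at d = 2 would bring the mean to (76 × 0.16 − 4 × 2)/80 = 0.052 (p = 0.45), against 0.16 (p = 0.0008) in completers alone. A scored mean therefore rests on grades that nobody observed, while a count does not.

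**The case against.** **The group may be empty.** Eligibility includes this criterion: "Demonstrates an acceptable fit with the study lenses". Section 9.2.1 adds a suitability check: "All subjects will be trial fitted and, if suitable, dispensed the MyDay Sphere and the MyDay Energys lens brand". Table 1 gives both lenses the same material, water content, base curve, diameter and power range. A fit-related stop in the following 7 to 10 days could well be rare. This stands: no figure in the documents supports one stop or four, and section 3 of the working is illustration only.

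**The text is partly hidden.** Visits 4 to 6 are incomplete in the public version. Visit 2, the parallel dispensing visit for Sphere, includes a fit grade, so Visit 4 may too, and section 13 mentions an unscheduled-visit form. No visit is named for the primary comparison, so Visit 5 is an inference. This also stands as a limit. But a grade at dispensing or early exit would not be a one-week grade, and no visible rule brings one into the analysis.

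**The hypothesis concerns grades only.** True, and the paired test can remain primary. It does not by itself answer the aim in section 2.

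**Stronger readings that the documents do not support.**

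- A reader might infer that 11.1 contradicts 5.1 and 12.1. They can largely be read together: everyone evaluated by default, with the cohort confirmed in a data-integrity discussion. What is missing is the exclusion rule.
- A reader might infer a conflict over when Energys is fitted, because Table 2 allows extra time at Visit 1 for fitting both lenses. The table does not say which two lenses, the Visit 1 procedures are partly hidden, and 9.3.4 places Energys at Visit 4: "At this visit, MyDay Energys will be fit dispensed".

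**Conclusion.** The point holds in a limited form. On the visible text, and taking Visit 5 as the one-week assessment, a fit-related stop before Visit 5 leaves the paired comparison and is counted nowhere as a failed refit. The size is unknown and may be zero. Four stops among 80 would mean 95.0% (87.7 to 98.6) where completers alone could show 100%, assuming every completer is successful.

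A reader might go further and infer that the primary result is biased or that failures are concealed. The documents do not support that. They give no number of stops, discontinuations are recorded with reasons, and the planned losses are within the sample size. The cohort point is likewise one of missing criteria in an unmasked study, not evidence of selective exclusion. This is a worthwhile, inexpensive improvement, held with medium confidence because of the hidden text.

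**What to change.** In 11.1:

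1. Name Visit 3 (Sphere) versus Visit 5 (Energys) as the primary contrast. Keep every participant with both grades in the primary paired analysis. Confine deviation-based exclusions to a sensitivity analysis, and align 5.1 and 12.1 with this.
2. Add a supporting result: the number and proportion successfully refit among all participants dispensed Energys, with an exact 95% CI, counting fit-related discontinuations as not successful. Before data lock, fix the success threshold on the Visit 5 grade and how the two eyes are combined. List all discontinuations by reason.

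Assigning grades to lost participants is not needed. The cost is some SAP wording, one proportion, one listing and one sensitivity analysis. The discontinuation reasons are already collected, and no visit or data item is added. The downside is slightly more analysis and a possibly less favourable result.

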## **12 Data Quality Assurance**

---

### **12.1 Study monitoring**

---

A site visit or discussion may be conducted during the course of the study as appropriate. Prior to final data lock, a close-out visit/discussion may be warranted to check for accuracy and completeness of records. Prior to data export for analysis there will be a discussion to confirm the cohort to be analyzed, with specific discussion around the data integrity in cases of protocol deviations and adverse events. The sponsor or sponsor's representatives will be authorized to gain access to the source documentation for the purposes of monitoring and auditing the study.

### **12.2 Record keeping**

---

Detailed records of all study visits will be made using the paper Case Report Forms (CRFs). Each subject will be identified on the CRFs with a study ID number which will not contain any identifying information such as initials and date of birth.

### **12.3 Record retention**

---

Following study completion, data will be available in electronic and/or paper format for audit, sponsor use, or subsequent analysis. The original clinical raw data (including completed CRFs and Informed Consent forms) will be retained according to guidelines set forth in the general work agreement with the site. After the study closeout visit, the sites will send the original CRFs to the sponsor. The Sponsor will be notified and consulted if ever the files are to be destroyed. In the event that this implementation document is indicated for design verification and validation purposes, as indicated on the title page, all original raw data forms and completed CRF's will be forwarded to the sponsor at completion of the final report.

